5. Researcher: noted down the time taken for confirmation by both methods. Also inspected for changes in vitals that would exclude the participant out of the study.

Inside the operating room the ultrasound machine was kept on the left hand side and in line with pelvis of the patient. The ultrasound operator was on the right hand side of the patient and in line with patient's xiphisternum. The blinding was done such that

the person reading capnogram would face away from the ultrasound machine, and the ultrasound operator would be facing away from the capnograph monitor.

Patient was placed supine comfortably in the operating table. Continuous ECG and SPO₂ monitoring, 5 minute interval NIBP monitoring or continuous invasive blood pressure monitoring when available was done. A running intravenous drip of crystalloid solution; Ringer's Lactate, Normal saline or Plasmalyte as required was started. Injection Fentanyl 2 microgram per kg was given intravenously. Then Injection Propofol 2 milligram per kg was given intravenously in TUTH and non-cardiac surgery patients in MCVTC, and Injection Etomidate 0.3mg per kg intravenously was given to cardiac surgery patients in MCVTC for induction. Induction of anaesthesia was complete after patient became unresponsive with central mid-dilated pupil and absence of eye lash reflex.

Manual bag and mask ventilation adequacy was then checked. Injection Vecuronium 0.1 milligram per kg was given intravenously, and the stopwatch was started. Manual bag and mask ventilation was continued by the primary intubating resident and assisted by the supervising anaesthesia faculty as needed.

High frequency linear ultrasound probe, 9-13 Megahertz, was placed transversely just above the suprasternal notch. The probe was shifted slightly cranially or caudally as needed to obtain the best visualization of trachea and oesophagus in the same image.

After 5 minutes of injecting Vecuronium, the researcher reset his stopwatch and announced "start" loudly (start point). Laryngoscopy and tracheal intubation was done by the anaesthesia resident. The ultrasound operator held the probe in the appropriate place as previously determined. If the position of the probe obstructed laryngoscopy,

the probe was shifted caudally and tilted slightly cranially. The study was continued only if the latter ultrasound image could also visualize both trachea and oesophagus.

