Participants were also excluded if there was:

- Unanticipated difficult bag and mask ventilation
- Unanticipated difficult intubation or CL grade 3 and 4 cases, use of bougie for intubation.
- Fall in Spo₂ (< 90%) before endotracheal tube position confirmation
- Bradycardia (heart rate < 40 beats/min) or hypotension (mean arterial pressure < 60 mm of Hg, systolic blood pressure < 80 mm of Hg) during or prior to intubation
- Tachycardia more than 120 bpm or blood pressure more than 180 mm Hg systolic or 110 mm Hg diastolic during or prior to intubation

There were 36 participants enrolled at MCVTC, out of which 5 of the participants had to be excluded out of the study. One had unanticipated difficult intubation, and the other four had hypotension after induction of anaesthesia. There were 67 participants

enrolled at TUTH, out of which 3 participants had to be excluded out of the study. Two subjects had hypotension after induction of anaesthesia. The other one had to be excluded because the ultrasound machine went into hung state. Thus there were 31 subjects from MCVTC and 64 subjects from TUTH. Data collection was terminated once the sample size of 95 was met. Different individuals operated ultrasound on the subjects in this study. Flow diagram of the study is shown in figure 8.

Operational Definitions

Ultrasound positive: meant ultrasound detected tracheal intubation. There was fluttering and movement inside the tracheal acoustic shadow as the endotracheal tube was passed, and by the completion of intubation there was only one comet tail appearing acoustic shadow. Color Doppler ray showed color change inside the acoustic shadow on shaking the endotracheal tube.

Ultrasound negative: meant ultrasound detected oesophageal intubation. There was fluttering and increase in echogenicity in the region of oesophagus as the endotracheal tube was passed. By the completion of intubation, there were two comet tail appearing acoustic shadows, “double-tract sign”. Color Doppler ray was seen outside the trachea on shaking the endotracheal tube.

Capnograph positive: meant capnogram showed regular normal shaped waveforms after 6 ventilations. The outcome was tracheal intubation.

Capnograph negative: meant oesophageal intubation. The capnogram had no waveforms or irregular, bizarre or non-uniform shaped waveforms after 6 ventilations.

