The median operating time of static post-intubation ultrasound was found to be 9 seconds with IQR [6 – 14 sec] by Chou et al²⁸ in their study. This was significantly faster than transcricothyroid static ultrasound for endotracheal tube confirmation done by Adi et al³⁰; their median time was 16.40 seconds. The results of these studies cannot be compared with this study because the beginning of laryngoscopy was taken as the start point for time assessment in this study. These studies started their assessment after intubation. The time for laryngoscopy is directly operator dependent and thus the time taken for assessment of endotracheal tube position directly increases with more time spent on doing laryngoscopy and intubation in this study.

Capnography

The sensitivity and specificity of capnography to detect endotracheal tube position was found to be 96.43% and 100% respectively in this study. This was similar to aggregate sensitivity and specificity of 93% and 97% found by Li in his meta-analysis.²⁴ This meta-analysis included trials which used any form of end tidal CO₂ detection device in adult human subjects. We have used only waveform capnography which is the gold standard; colorimetric and quantitative ET_{CO}₂ are less accurate than waveform capnography.^{3,7,8,12}

There were three false negative results in capnography. Two of the three false negative results occurred while using sidestream capnography at TUTH and the other false negative result occurred at MCVTC which also had sidestream capnography. There were more than two irregular waveforms during the first six ventilations in these false negative cases.

The false negatives might have occurred in the sidestream capnographs because these are more likely to be blocked due to fogging or misting^{2,7} such that the sampling line gas flow could have been obstructed. At MCVTC, after about 15 irregular waveforms, there was no waveform seen for about the next 90 seconds followed by presence of regular waveforms thereafter. This might be due to auto calibration of the capnograph, the occurrence of which during intubation might have produced false negative result.

Other causes like compromised pulmonary blood flow and bronchospasm can also lead to false negative results.^{3,9,10} Patients who had hypotension after induction of anaesthesia that could lead to compromised pulmonary flow, were excluded from this study. Bronchospasm would be identified by auscultation or high peak airway

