This study used both sidestream and mainstream capnographs. This was because of availability of different types of capnograph at the study sites. The details of sampling line delay are discussed later.

Ultrasonography vs Capnography

Both ultrasonography and waveform capnography were found to be good, reliable and fairly accurate diagnostic methods of confirming endotracheal tube position. Though ultrasonography and capnography were equally sensitive and capnography seemed more specific; the sensitivity, specificity, PPV, NPV of ultrasonography were comparable (statistically not different as seen by their confidence intervals) to waveform capnography.

The combination of ultrasonography and capnography increased precision (accuracy) over using either one of them in this study. Since the studies done previously had compared ultrasonography against capnography as the standard and thus calculated the sensitivity, specificity, PPV, NPV of ultrasound; these were not able to show if ultrasound had increased accuracy over using capnography alone.

Both of these methods are now known to be equally reliable. Hence in case of unmatched result given by these two methods in a patient, a third highly reliable method of confirmation has to be used because both ultrasonography and capnography have statistically not different false positive (1 – specificity) and false negative (1 – sensitivity) rates.

There was generally good agreement between the results produced by ultrasonography and capnography as shown by the kappa value of 0.749 with 95% confidence interval of (0.567 – 0.931). Other studies have shown a good or a very good agreement of these two methods by kappa statistics. The kappa value calculated by Adi et al³⁰, Chou et al²⁸, Karacebay et al²⁷ and Chintamani et al³⁴ were 0.85, 0.93 (0.84 – 1.00), 0.85 and 0.76 respectively.

Real-time, transtracheal, transverse suprasternal ultrasonography was significantly faster ($p = 0.011$) than capnography by 16.36 ± 3.23 seconds (mean \pm SD) in confirming endotracheal tube position in this study. The subgroup analysis between mainstream and sidestream capnographs also showed that the type of waveform capnograph device used did not affect the significant difference in time of ultrasound over capnograph in confirming endotracheal tube position.

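### An ultrasound machine failure was excluded without a listed criterion while unreadable capnograms were scored as results, so ultrasound accuracy assumes a working machine and the reported tie can turn on one patient

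*Combined protocol and SAP*

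**What the plan says.** All references are to the combined protocol and SAP.

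- **Exclusions.** The Exclusion criteria and the in-procedure list in Materials and Methods cover patient, airway, oxygenation and haemodynamic reasons. Neither names equipment failure for either method.
- **Ultrasound hang.** Of 103 enrolled (36 at MCVTC, 67 at TUTH), eight were excluded: one for difficult intubation, six for hypotension, and one TUTH participant for whom the stated reason is "The other one had to be excluded because the ultrasound machine went into hung state". That patient's tube position and capnography result are not given.
- **Lost ultrasound view.** When the probe had to be moved for laryngoscopy, Materials and Methods says: "The study was continued only if the latter ultrasound image could also visualize both trachea and oesophagus".
- **Unreadable capnogram.** Operational Definitions scores this as a result. A negative capnograph is defined so: "The capnogram had no waveforms or irregular, bizarre or non-uniform shaped waveforms after 6 ventilations".
- **Capnograph event.** Discussion, Capnography, describes one of the three false negatives: "At MCVTC, after about 15 irregular waveforms, there was no waveform seen for about the next 90 seconds followed by presence of regular waveforms thereafter". The explanation offered is: "This might be due to auto calibration of the capnograph, the occurrence of which during intubation might have produced false negative result". The patient stays in Table 9 as a capnography error.
- **Comparison.** Table 10 gives accuracy of 96.84% for both methods. The Conclusion states that the two are equal in reliability and accuracy. Limitations does not mention how device events were handled, and no sensitivity analysis is shown.

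**The concern.** An ultrasound that yields no reading leaves the study. A capnograph that yields no readable wave stays in and counts as a call of oesophageal placement. The two denominators therefore mean different things: ultrasound performance is conditional on a working machine and a visible trachea and oesophagus, whereas capnography performance includes unreadable traces.

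With three errors per method, one patient is enough to make or break the tie in accuracy. A reader choosing a method for routine use also needs to know how often it gives no answer, and Table 10 leaves that out.

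**Working it through.** **Inputs.** Table 8, ultrasound: TP 82, FP 1, FN 2, TN 10. Table 9, capnography: TP 81, FP 0, FN 3, TN 11. Results states that each of the 84 tracheal tubes was identified by at least one method, so the false negatives do not overlap and ultrasound was right in the MCVTC patient. The reported kappa of 0.749 matches no overlap pattern exactly, but is nearer to the value for no overlap (0.733) than to that for one shared false negative (0.822).

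**Formulas (from Methodology).** Sensitivity = TP/(TP+FN); NPV = TN/(TN+FN); accuracy = (TP+TN)/N.

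**Step 1: reproduce Table 10.**

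| | Ultrasound | Capnography |
|---|---|---|
| Accuracy | 92/95 = 96.84% | 92/95 = 96.84% |
| Sensitivity | 82/84 = 97.62% | 81/84 = 96.43% |
| NPV | 10/12 = 83.33% | 11/14 = 78.57% |

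All six figures agree with the document.

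**Step 2: keep both device events and count the hang as an ultrasound failure, N = 95 + 1 = 96.** Ultrasound accuracy is 92/96 = 95.83% in every case. The rest depends on two unreported facts. In this table the hang is scored as a wrong ultrasound call.

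| Hang patient: tube; capnography | Accuracy, US v capnography | Sensitivity, US v capnography | NPV, US v capnography |
|---|---|---|---|
| Trachea; right | 92/96 v 93/96 (96.88%) | 82/85 v 82/85 (96.47% both) | 10/13 = 76.92% v 11/14 = 78.57% |
| Trachea; wrong | 92/96 v 92/96 | 82/85 = 96.47% v 81/85 = 95.29% | 10/13 = 76.92% v 11/15 = 73.33% |
| Oesophagus; right | 92/96 v 93/96 | 82/84 = 97.62% v 81/84 = 96.43% | 10/12 = 83.33% v 12/15 = 80.00% |
| Oesophagus; wrong | 92/96 v 92/96 | 82/84 = 97.62% v 81/84 = 96.43% | 10/12 = 83.33% v 11/14 = 78.57% |

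Ultrasound never leads on accuracy, but it leads on sensitivity in three of the four cases. In the first case, scoring the hang as no call instead of a negative call gives NPV 10/12 = 83.33% v 78.57%, so ultrasound leads there too.

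**Step 3: exclude both device events, N = 95 − 1 = 94.** Removing the MCVTC patient takes one TP from ultrasound and one FN from capnography.

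| | Ultrasound | Capnography |
|---|---|---|
| Accuracy | 91/94 = 96.81% | 92/94 = 97.87% |
| Sensitivity | 81/83 = 97.59% | 81/83 = 97.59% |
| NPV | 10/12 = 83.33% | 11/13 = 84.62% |

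The accuracy tie breaks, the sensitivity lead goes and the NPV order reverses.

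**Step 4: test the paired differences.** With no overlap, the discordant counts (ultrasound errors v capnography errors) are 2 v 3 for sensitivity and 3 v 3 for accuracy as reported, and 2 v 2 and 3 v 2 after Step 3. Exact McNemar p = 1.0 in all four; for 2 v 3, p = 2 × 16/32 = 1.0.

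**Step 5: timing of the capnograph event.** At 26 ventilations per minute, six take 6 × 60/26 = 13.8 s and fifteen take 15 × 60/26 = 34.6 s. The blank period came after about fifteen waves, and so after the six-ventilation reading.

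**The case against.** **The events are not equivalent.** The hang has no reported ultrasound result. The MCVTC capnograph gave a definite reading that met the definition of negative before the trace went blank. Of the capnography false negatives the document says: "There were more than two irregular waveforms during the first six ventilations in these false negative cases". Auto-calibration is only a hedged explanation after the fact, and dropping a completed wrong reading on that ground is itself outcome-dependent and favours capnography. This stands, and it is why Step 3 can only be a sensitivity analysis.

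**Ultrasound is not shielded from every failure.** Discussion, Ultrasonography, describes unclear post-intubation images in all three ultrasound errors, and all three were scored as errors. No patient is reported lost under the lost-view rule: the eight exclusions have other reasons, and all six probe adjustments stayed in. Other exclusions protect capnography. Six patients left for hypotension, which the Discussion links to capnography false negatives through low pulmonary flow. So a reader may not infer a bias running in one direction throughout.

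**The document claims no accuracy lead for ultrasound.** Discussion, Ultrasonography vs Capnography, says: "Though ultrasonography and capnography were equally sensitive and capnography seemed more specific". It calls the differences statistically indistinguishable, and ultrasound's claimed advantage is time. That is fair, but the Conclusion's claim of equal accuracy still rests on the unexplained denominator.

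**The data may not exist.** The reference standard used lung sliding on ultrasound, and only one ultrasound machine is described for TUTH. The timing of the hang is not stated; if it came before laryngoscopy, no index test took place. This limits the fix but does not remove the need to report the failure.

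**Conclusion.** The point holds as one of handling and reporting. An enrolled patient was removed for an ultrasound machine failure under no listed criterion, and the lost-view rule works the same way by design, while unreadable capnograms are scored. Counting the hang as a failure lowers ultrasound accuracy from 96.84% to 95.83%, about one percentage point, against 95.83% to 96.88% for capnography. Excluding both device events gives 96.81% against 97.87%.

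These figures assume that the hang occurred during the test, that the patient met all other criteria, and that the false negatives do not overlap, as Results states.

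A reader might infer that under any even-handed rule ultrasound leads on nothing, or that capnography is the better method. The documents support neither. When both events are counted, ultrasound may keep its leads in sensitivity and NPV, depending on data not reported. No difference approaches significance. What is shown is that the tie is fragile.

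**What to change.** 1. State one rule for device failures and non-results and apply it to both methods. A machine failure or lost view is recorded as inconclusive and kept in that method's denominator.
2. Report when the hang occurred and, if a reference result was obtained, the patient's tube position and capnography result, and add the patient to the main tabulation. If none was obtained, give the technical-failure rate of 1 in 96 beside Table 10.
3. State how many patients were lost under the lost-view rule, even if none.
4. Add a sensitivity version of Table 10 excluding both device events, noting that the auto-calibration explanation is tentative.
5. Disclose the handling under Limitations, and qualify the claim of equal reliability and accuracy as applying when both devices gave a usable reading.

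The cost is re-tabulating one or two patients. Ultrasound accuracy falls by about one percentage point if the hang counts as a failure. The hang patient's reference result may not be recoverable, in which case only the failure rate can be given.

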After confirmation of the endotracheal tube position, true and false positives and negatives were determined for both the methods as depicted in table 1.

Sensitivity, specificity, positive predictive value and negative predictive value, likelihood ratios; for both ultrasonography and capnography were calculated using their corresponding formulas.³⁷ The results were extrapolated into confidence intervals using Clopper-Pearson confidence interval.³⁷

Table 1. Designation of true and false positives and negatives.

Capnography		Ultrasonography	
Tracheal outcome	Oesophageal outcome	Tracheal outcome	Oesophageal outcome
True positive (TP): final position in trachea.	True negative (TN): final position in oesophagus.	True positive (TP): final position in trachea.	True negative (TN): final position in oesophagus.
False positive (FP): final position in oesophagus.	False negative (FN): final position in trachea.	False positive (FP): final position in oesophagus.	False negative (FN): final position in trachea.

Sensitivity = TP / (TP+FN).

Specificity = TN / (TN+FP).

Positive predictive value (PPV) = TP / (TP+FP).

Negative predictive value (NPV) = TN / (TN+FN).

Confidence intervals, CI (at 95 % level of confidence): for example for sensitivity

CI = (Sensitivity + 1.96SE, sensitivity – 1.96SE). Where SE is standard error,

SE for sensitivity = square root of [sensitivity (1 – sensitivity)/(TP+FN)]³⁷

Accuracy = $(TP+TN) / (TP+TN+FP+FN)$.

(TP=True Positive, TN=True Negative, FP=False Positive, FN= False Negative)

Likelihood ratio of a positive test: was given by

$$LR_{+} = \frac{\text{sensitivity}}{1 - \text{specificity}}$$

The positive likelihood ratio values corresponded to different probabilities as follows³⁷:

Table 2. Interpretation of positive likelihood ratio.³⁷

Positive likelihood ratio value	Probability
0	Excluded disease.
> 10	Large change in likelihood (or in other words high probability of any individual having a positive result on using the diagnostic test).
5 – 10	Moderate change in likelihood.
2 – 5	Small change in likelihood.
1	No change.

Likelihood ratio of negative test: was given by

$$LR_{-} = \frac{1 - \text{sensitivity}}{\text{specificity}}$$

The negative likelihood ratio values also corresponded to different probabilities as follows³⁷:

Table 3. Interpretation of negative likelihood ratio.³⁷

Negative likelihood ratio value	Probability
infinity	Excluded normality.

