Among the 95 subjects, the mean age was found out to be 44.24 years with standard deviation of ± 16.18 years, and the median age was 47 years. The youngest patient was of 16 years, and the eldest patient was 85 years old. Most patients were in the age group of 41 to 50 years.

Table 5. Demographic profile according to age.

Mean \pm SD (in yrs)	Median (in yrs)	Maximum (in yrs)	Minimum (in yrs)
44.24 \pm 16.18	47	85	16

(n=number, SD= Standard Deviation, yrs = years)

[figure not shown]

Fig. 9. Distribution of the subjects into different age groups.

Among the 95 subjects, there were 51 females (53.68%) and 44 males (46.32%) in this study.

[figure not shown]

Fig. 10. Sex-wise profile of patients in the study.

The majority of patients were Brahmins (40%), followed by Chhetris (22.10%), Newars (14.70%), Magars (7.36%), and others (15.84%); as shown in figure 11. Others include Rai (4), Bhaisnav (1), Chaudhary (1), Muslim communities (2), Lama (2), Gurung (1), Damai (1), Tamang (2), Thakuri (1) and Sherpa (1).

BMI

The mean body mass index (BMI) of the 95 patients was found to be 23.55 ± 3.58 (mean \pm standard deviation); the median BMI was 23.72 and the inter-quartile range [20.68 - 25.92], all values expressed in kg/m^2 . The summary is shown in table 3 and figure 12.

[figure not shown]

Fig. 11. Distribution of patients as per ethnicity in this study.

Table 6. Average body mass index (BMI) of patients.

	Mean \pm SD	Range	Median	IQR
BMI (kg/m^2)	23.55 \pm 3.58	16.33 - 33.88	23.72	[20.68 - 25.92]

(SD = Standard Deviation, Range = Maximum - minimum values; IQR = Interquartile range)

[figure not shown]

Fig. 12. Frequency of patients according to WHO classification of BMI.

ASA Physical Status

There were 46 ASA I patients and 49 ASA II patients in this study. The clinical conditions in patients with ASA II status are listed below in table 4. Table 4 does not account for the presence of multiple clinical conditions in the patients.

[figure not shown]

Fig. 13. ASA Physical status distribution of patients.

Table 7. Clinical conditions in ASA II patients.

	No. of patients	
	MCTVC	TUTH
Valvular heart disease	8	0
Coronary heart disease	14	1
Vascular disease	6	0
Hypertension	14	6
Diabetes Mellitus	4	1
Hypothyroidism	3	3
Hepatitis C positive	0	1
Central nervous system disease	0	8

Analytical Statistics and Data

Out of the total 95 intubations, there were 11 oesophageal intubations. The incidence of oesophageal intubation was 11.57% in this study.

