Ultrasonography

Ultrasound falsely detected one oesophageal intubation as tracheal, and two tracheal intubations as oesophageal.

Table 8. Distribution of positives and negatives for ultrasonography.

Position showed by Ultrasound	Endotracheal tube position confirmation		Total
	Trachea	Oesophagus	
Trachea (n)	TP = 82	FP = 1	83
Oesophagus (n)	FN = 2	TN = 10	12
Total	84	11	n = 95

(n=no. of patients, TP=True Positives, FP=False Positives, FN=False Negatives, TN=True Negatives)

The sensitivity, specificity, positive predictive value and negative predictive value (with their corresponding 95% confidence intervals in round brackets) were calculated to be 97.62% (91.66% - 99.71%), 90.91% (58.72% - 99.77%), 98.80% (92.67% - 99.81%) and 83.33% (55.66% - 95.22%) respectively. The positive likelihood ratio was 10.74, which suggested a large change in the likelihood of positive result. The negative likelihood ratio was 0.03 which also suggested a large change in the likelihood of negative result. The accuracy of ultrasonography in confirming endotracheal tube placement was 96.84% (92.92% - 100%).

[figure not shown]

Fig. 14. Distribution of positives and negatives for ultrasonography.

Capnography

There were three false negative results given by waveform capnography. There was no false positive result.

Table 9. Distribution of positives and negatives for capnography.

Position showed by waveform capnography	Endotracheal tube position confirmation		Total
	Trachea	Oesophagus	
Trachea (n)	TP = 81	FP = 0	81
Oesophagus (n)	FN = 3	TN = 11	14
Total	84	11	n=95

(n=no. of patients, TP=True Positives, FP=False Positives, FN=False Negatives, TN=True Negatives)

[figure not shown]

Fig. 15. Distribution of positives and negatives for capnography.

The sensitivity, specificity, positive predictive value and negative predictive value (with their corresponding 95% confidence intervals in round brackets) of capnography were calculated to be 96.43% (89.92% - 99.26%), 100% (71.51% - 100%), 100% (100% - 100%) and 78.57% (54.69% - 91.76%) respectively. The positive likelihood ratio was infinity. The negative likelihood ratio was 0.04 which suggested a large change in the likelihood of negative result. The accuracy of capnography in confirming endotracheal tube placement was 96.84% (92.92% - 100%).

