Both ultrasonography and waveform capnography were found to be good, reliable and fairly accurate diagnostic methods of confirming endotracheal tube position. Ultrasonography was comparable diagnostically with capnography for endotracheal tube confirmation. The comparisons of the pretest and posttest probabilities of the two methods are shown in table 10.

Table 10. Comparison of the diagnostic characteristics of ultrasonography and waveform capnography.

	Ultrasonography	Waveform Capnography
Sensitivity in % (95% CI)	97.62 (91.66- 99.71)	96.43 (89.92 - 99.26)
Specificity in % (95% CI)	90.91 (58.72 - 99.77)	100 (71.51 - 100)
PPV in % (95% CI)	98.80 (92.67- 99.81)	100 (100 – 100)
NPV in % (95% CI)	83.33 (55.66 - 95.22)	78.57 (54.69 - 91.76)
Accuracy in % (95% CI)	96.84 (92.92 - 100)	96.84 (92.92 - 100)
Positive likelihood ratio	10.74	Infinity
Negative likelihood ratio	0.03	0.04

(CI= Confidence Interval, PPV= Positive Predictive Value, NPV= Negative Predictive Value)

Both ultrasonography and capnography together had correctly identified 10 out of the 11 oesophageal intubations. The 84 tracheal intubations were correctly identified by both ultrasonography and capnography or either one of these methods. Using the same formula (page 35), the combined accuracy of both the methods together was 98.94% (94 divided by 95, in percentage).

The analysis of agreement between the ultrasonography and capnography results was done using Cohen's kappa statistics. A kappa value of 0.749 with 95% confidence interval of (0.567 – 0.931) and standard error of 0.093 was found. The kappa value therefore showed a good agreement between the result of these two methods.

Time taken for endotracheal tube confirmation

Real-time ultrasonography was faster than waveform capnography for endotracheal tube confirmation in all cases. The mean time for confirmation by ultrasonography was 26.79 ± 7.64 seconds (mean \pm standard deviation). The mean time for confirmation by capnography was 43.03 ± 8.71 seconds.

The mean difference in time was 16.36 seconds (95% CI: 15.70sec – 17.02 sec). The median difference in time was 16 seconds. The standard deviation in difference in time was 3.23 seconds. The standard error of mean (SEM) was 0.332 seconds. The difference in time was highly significant ($p = 0.011$).

Table 11. Time taken for endotracheal tube confirmation.

	Range (in seconds)	Mean \pm SD (in seconds)	Median (in seconds)	IQR (in seconds)	p-value

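### The Methodology gives two incompatible interval rules, and Table 10 mixes at least three methods: the NPV intervals are 6.8 and 9.1 points narrower than the named exact method gives, and one PPV interval has zero width

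*Combined protocol and SAP*

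**What the plan says.** In the Methodology, after Operational Definitions, one sentence lists sensitivity, specificity, PPV, NPV and likelihood ratios for both methods. The next reads: "The results were extrapolated into confidence intervals using Clopper-Pearson confidence interval". Exact intervals are therefore declared for the predictive values as well.

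Below Table 1 a second rule appears under "Confidence intervals, CI (at 95 % level of confidence", with sensitivity as the worked example: "CI = (Sensitivity + 1.96SE, sensitivity – 1.96SE". Its standard error is the usual binomial one. The Statistical Analysis section adds only that the quantities and their intervals were programmed in Excel. No other interval method is named.

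Table 10 prints the ultrasound NPV as "83.33 (55.66 - 95.22" and the capnography NPV as "78.57 (54.69 - 91.76". The predictive-value intervals for both methods also stand in the Abstract and in the Results text around Tables 8 and 9. The ultrasound ones are repeated in the Discussion. The accuracy interval is printed in the Results text and in Table 10.

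**The concern.** With 11 oesophageal intubations, and 12 and 14 oesophagus calls, the two rules give very different answers, and the 1.96 SE rule can run past 100%. A reader cannot tell which rule produced which row of Table 10.

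The NPV says how far to trust a call that the tube is in the oesophagus. The Discussion also reasons directly from these intervals. It says the two methods do not differ statistically on sensitivity, specificity, PPV or NPV, judging by their confidence intervals. It also calls the ultrasound NPV interval comparable with earlier published NPVs. Both statements depend on which method produced the limits.

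**Working it through.** **Inputs.** "Out of the total 95 intubations, there were 11 oesophageal intubations", so 84 were tracheal. "Ultrasound falsely detected one oesophageal intubation as tracheal, and two tracheal intubations as oesophageal", so for ultrasound TP = 82, FP = 1, FN = 2, TN = 10 (Table 8). For capnography TP = 81, FP = 0, FN = 3, TN = 11 (Table 9).

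**Step 1: intervals that reproduce.** Clopper-Pearson limits for x out of n are the 2.5% quantile of Beta(x, n − x + 1) and the 97.5% quantile of Beta(x + 1, n − x). They give all four sensitivity and specificity intervals as printed:

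- Ultrasound sensitivity, 82/84: 91.66-99.71.
- Ultrasound specificity, 10/11: 58.72-99.77.
- Capnography sensitivity, 81/84: 89.92-99.26.
- Capnography specificity, 11/11: 71.51-100.

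The second rule was not used even for its own example. For ultrasound sensitivity, SE = √(0.9762 × 0.0238 / 84) = 0.0166, giving 94.36-100.88. For ultrasound specificity it would give 73.92-107.90.

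**Step 2: intervals that are not exact.**

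| Quantity | Count | Printed | Clopper-Pearson | ± 1.96 SE |
|---|---|---|---|---|
| Ultrasound PPV | 82/83 | 92.67-99.81 | 93.47-99.97 | 96.45-101.14 |
| Ultrasound NPV | 10/12 | 55.66-95.22 | 51.59-97.91 | 62.25-104.42 |
| Capnography PPV | 81/81 | 100-100 | 95.55-100 | 100-100 |
| Capnography NPV | 11/14 | 54.69-91.76 | 49.20-95.34 | 57.08-100.07 |
| Accuracy, each method | 92/95 | 92.92-100 | 91.05-99.34 | 93.33-100.36 |

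**Step 3: where the printed values come from.** Take a logit interval for predictive values, built from sensitivity and specificity with the sample prevalence treated as known.

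- logit(NPV) = ln(TN/FN), variance = [sens/(1 − sens)]/84 + [(1 − spec)/spec]/11.
- logit(PPV) = ln(TP/FP), variance = [(1 − sens)/sens]/84 + [spec/(1 − spec)]/11.

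Putting the counts in:

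- Ultrasound NPV: ln(10/2) = 1.609; variance = 41/84 + 0.1/11 = 0.497; 1.609 ± 1.96 × 0.705 gives 55.66-95.22.
- Capnography NPV: ln(11/3) = 1.299; variance = 27/84 + 0 = 0.321; 1.299 ± 1.96 × 0.567 gives 54.69-91.76.
- Ultrasound PPV: ln(82/1) = 4.407; variance = 0.0003 + 10/11 = 0.909; 4.407 ± 1.96 × 0.954 gives 92.67-99.81.

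All three agree with print to two decimals. With FP = 0 this method is undefined for capnography PPV, and the printed 100-100 equals the degenerate 1.96 SE interval. For accuracy, the unrounded SE is √(0.9684 × 0.0316 / 95) = 0.0179. Rounded to 0.02, the lower limit is 96.84 − 1.96 × 2 = 92.92, as printed, with the upper limit cut at 100.

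**Step 4: size against the exact method.**

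- Ultrasound NPV width: 39.56 printed, 46.33 exact, so 6.8 points too narrow.
- Capnography NPV width: 37.07 printed, 46.14 exact, so 9.1 points too narrow.
- Ultrasound PPV width: 7.14 printed, 6.50 exact, so 0.6 points too wide.

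**Step 5: effect on the Discussion.** The printed PPV intervals, 92.67-99.81 and 100-100, do not overlap; the exact ones, 93.47-99.97 and 95.55-100, do. The printed upper limit for ultrasound NPV, 95.22, excludes the 96.77% of the earlier study that used neck X-ray as reference; the exact limit, 97.91, includes it.

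**The case against.** The strongest reply is that nothing here is miscalculated. The three logit intervals are correct under a recognised method, so one sentence naming it would cure the non-disclosure without changing a number. That is largely fair: the fault is undeclared mixing of methods. But such a sentence would leave the two stated rules in conflict, and the logit method cannot supply an interval for capnography PPV.

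It can also be said that Clopper-Pearson is a conservative yardstick. At the observed values its coverage is about 99% for n = 12 and 98% for n = 14, and the Wilson interval for 10/12 is 55.20-95.30, almost the printed one. This stands. The NPV intervals are too narrow relative to the method the document names, not indefensible as 95% intervals.

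A reader might go further and infer that uncertainty is understated for all the predictive values. It is not: the ultrasound PPV interval is wider than exact, and PPV rests on 83 and 81 calls. Nor does the mix make Table 10 useless for comparing the two methods. The sensitivity, specificity, NPV and accuracy rows each use one method across both columns; only the PPV row does not.

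Finally, the exact intervals help the authors' two Discussion statements. That is true, but as printed the limits contradict those statements.

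**Conclusion.** The point holds as an inconsistency between stated and applied methods, of moderate weight. Two rules are declared. Sensitivity and specificity follow the first, three predictive-value intervals follow neither, capnography PPV has zero width, and accuracy appears to follow a rounded form of the second. The largest effect is on capnography NPV, whose lower limit moves from 54.69% to 49.20%, although the documents attach no threshold to 50%.

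This rests on the counts in Tables 8 and 9 and on taking the Clopper-Pearson sentence to cover the predictive values listed just before it. Accuracy is not in that list, so for accuracy the fault is an unstated method and a rounded SE. The origins of the logit and accuracy intervals are inferred from numerical agreement; the document does not state them.

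A reader might infer from the non-overlapping printed PPV intervals that the two methods differ in PPV. The documents do not support that: the non-overlap comes from the zero-width interval. Overlap of the exact intervals would not prove equality either.

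**What to change.** Delete the 1.96 SE formula below Table 1 and state that Clopper-Pearson is used for every proportion, accuracy included. Then reprint the non-exact intervals wherever they appear (Abstract, Results text, Table 10, and the Ultrasonography part of the Discussion):

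- Ultrasound PPV 93.47-99.97 and NPV 51.59-97.91.
- Capnography PPV 95.55-100 and NPV 49.20-95.34.
- Accuracy, both methods, 91.05-99.34.

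Recheck the two Discussion statements against the new limits. The cost is one deleted formula, one clarified sentence and six reprinted intervals, all from counts already in Tables 8 and 9. The downside is wider NPV intervals from a method that is conservative at these counts.
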